In this study, we will examine the association between tobacco use and COVID-19 vaccine uptake and between-dose spacing. Given conflicting results of previous studies, we expect to observe an association between tobacco use and vaccination uptake and dose-spacing, but the direction of the effect is unclear. We will expand current knowledge by examining two forms of tobacco use in Finland -smoking and smokeless tobacco use (snus)- and by analysing the spacing between vaccine doses. We will use data from nationally representative surveys in Finland linked to vaccination registries, which reduces the risk of selection and information bias.

Methods

The study protocol has been written in close accordance with the Strengthening the Reporting of Observational Studies in Epidemiology (STROBE) statement for cohort studies²⁷

Study design

The study design is a cohort study of nationally representative health surveys linked to COVID-19 vaccination data derived from the Finnish National Vaccination Register, using a unique personal identification number assigned to all residents in Finland.

Setting and participants

We will use data from two FinSote Surveys, which are cross-sectional population health surveys in Finland.

Participants in the FinSote 2018 Survey were adults aged 20 years and over derived from the Population Register of Statistics Finland, which comprises all residents in Finland. This sampling frame includes people living in institutions and military conscripts.²⁸ The survey

was based on stratified random sampling, one stratum for each 19 counties. In 2017, 3300 people were invited to participate from 18 research areas (2300 adults aged 20-74 and 1000 adults aged 75+, total sample size 59400). Data was collected between October 2, 2017, and March 3, 2018. Participants received a self-administered questionnaire in Finnish, Swedish, English or Russian, which could be returned on paper or filled in electronically. The participation rate was 45%, resulting in a total of 26422 participants.²⁸ Participants were asked for consent for registry linkage, resulting in an analytical sample of 14736 subjects.

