Participants in the FinSote 2020 Survey were adults aged 20 and over derived from the Digital and Population Data Services Registry, created in Jan 2020 after the merge between the Population Register of Statistics Finland and local register offices.²⁹ This sampling frame includes all residents in Finland. The survey was based on a stratified random sample of 22 regions (2000 adults aged 20-74, 800 adults aged 75+, total sample size 61600). Data collection started on September 14, 2020, and finished on February 8, 2021. Participants received a self-administered questionnaire in Finnish, Swedish, English or Russian, which could be returned on paper or filled in electronically. The analytical sample is 28199 participants, with a participation rate of 46%. In 2020, consent to linkage was included in the overall consent, and as a result, we were able to link all participants in the analytical sample.

We will link data from FinSote 2018 and 2020 surveys to the Finnish National Vaccination Register maintained by the Finnish Institute for Health and Welfare using a unique identifier assigned to all residents in Finland. The follow-up will be between December 27, 2020 (date of the first COVID-19 vaccination in the country) until May 31, 2022 or the latest available date.

Outcomes

Our primary outcome will be the vaccination uptake of at least two doses of a COVID-19 vaccine. We will examine four secondary outcomes:

- (i) vaccination uptake of at least one dose of a COVID-19 vaccine,
- (ii) vaccination uptake of the complete COVID-19 vaccination scheme (two doses and a booster dose),
- (iii) proportion of participants with more than 7 months between the first and second COVID-19 dose, and
- (iv) proportion of participants with more than 7 months between second dose and booster dose.

We will include any approved COVID-19 vaccination in Finland by the latest available date (i.e. April 29, 2022):³⁰ COVID-19 mRNA vaccines (Comirnaty and Spikevax), recombinant vaccines (Vaxzevria, COVID-19 vaccine Janssen, COVISHIELD, Nuvaxovid, COVOVAX), and inactivated vaccines (BIBP/Sinopharm, COVAXIN, Coronavac). Participants who have received the COVID-19 vaccine Janssen would be excluded from analyses on the second dose, as the vaccine only requires a single dose.

Exposures

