We will examine two forms of tobacco use: smoking and smokeless tobacco (snus) use. We will assess smoking status with the following question: Do you smoke currently (cigarettes, cigars or pipe)? (a) yes, daily, (b) occasionally, (c) not at all, (d) I have never smoked. We will create a categorical variable with the following categories: never smokers, former smokers, current occasional smokers and current daily smokers.

We will assess snus use with the following question: Do you currently use any of the following products? Snus (Swedish type moist stuff) (a) yes, daily, (b) occasionally, (c) not at all, (d) I have never used. We will create a categorical variable with the following categories: never users, former users, current users (daily and occasional combined). Data on smoking status is available for all participants, while data on snus use was available for participants aged 20-74 years old.

Potential confounders

We will adjust for several potential sociodemographic confounders: age, sex, marital status, educational tertile, and participation in social activities. All variables will be analysed at baseline. We will define marital status as those married or in a registered relationship or cohabiting versus those separated or divorced, widowed or single. We will calculate educational tertiles for each survey year using the years of education reported in the question “How many years altogether have you attended school or studied full time?”. We will analyse participants’ mother tongue using data from national registries and will categorise it into three categories: Finnish, Swedish and other. We will measure participation in social activities with a question about participation in the activities of any club, association, hobby group or religious or spiritual community. We will categorise participation into the following: no participation, occasional and active.

Potential mediators

We will take the incidence of COVID-19 infections into account (see below). We will obtain data on confirmed COVID-19 cases from the Finnish National Infectious Disease Register maintained by the Finnish Institute for Health and Welfare. Confirmed COVID-19 cases will be defined as those cases with a positive SARS-CoV-2 RT-PCR, either informed by a laboratory or by a physician as a record of an ICD-10 code U07.1 (which requires a positive SARS-CoV-2 RT-PCR). Reporting of COVID-19 positive cases was mandatory for laboratories and physicians throughout the study period.

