Effect modifiers

We will examine potential effect modification by reporting stratified results by age (as a categorical variable), sex and educational level.

Data sources and measurement

[figure not shown]
Data sources and measurements for all variables were described above. More details on the exact variables can be found in the Supplementary Appendix.

Bias

Confounding bias

We will reduce the risk of confounding by adjusting for potential confounders that causally precede the exposure and are associated with the outcome. We built a directed acyclic graph to guide the identification of potential confounders and mediators (Figure 1). Adjusting for mediators can result in an underestimation of the association and potentially introduce M-bias (a type of collider bias).^{31,32}

Figure 1. Directed acyclic graph of the causal association between tobacco use and COVID-19 vaccinations uptake

A special concern were participants who had a COVID-19 infection. Tobacco use is associated with COVID-19 infection and, in turn, having a COVID-19 infection can influence the willingness to vaccinate or delay COVID-19 vaccination. Current Finnish guidelines recommend to the general adult population, after having a COVID-19 infection, to: (i) wait at least two months before getting the first COVID-19 dose, (ii) wait at least four to six months after the COVID-19 infection or the first dose, whichever happens first. People with two doses will not be given a third dose if they have had COVID-19. Having a COVID-19 infection, according to our DAG, would act as a mediator. Excluding individuals who have had the infection (or adjusting for it) would result in estimating the direct effect between tobacco use and COVID-19 vaccination uptake and not the total effect. For this reason, our main analyses will report the outcomes without adjusting for having a COVID-19 infection. In sensitivity analyses, we will report estimates stratified by COVID-19 infection status and also we will use causal inference methods (e.g. marginal structural methods and G-formula) to account for this time-varying estimate. We expect, however, that this will not make a large difference, as the COVID-19 incidence prior to the start of the COVID-19 vaccinations was very low and continued to be low until the rise of the Omicron variant in mid-December 2021.³³ In practice, this means that a very small proportion of our sample will experience a COVID-19 infection during the study period.

Selection bias

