We described the categorisation of exposures and confounders above. We will model age as a continuous variable and tested non-linearity by comparing the linear model with penalised smoothing splines using a likelihood ratio test.³⁵ The variable years of education will be modelled as categorical to be able to account for secular changes in years of education during the study years. In other words, educational attainment increases over time and it is therefore more appropriate to calculate the educational attainment within each survey wave.

Statistical methods

We will use Poisson regression with robust standard errors to estimate the relative risk of confirmed COVID-19 cases. We will fit the following Poisson model:

$$(1) \quad \log \mu_i = \beta_0 + \beta_1 S_i + \beta_x X_i^* + \rho_1 R_a$$

where i denotes the individual, β_0 is the intercept; β_1 is the coefficient of interest for exposure to tobacco S ; a vector of covariates X^* (i.e., sex, age, marital status, years of education, mother tongue and participation in social activities); and fixed effects $\rho_1 R_a$ for wellbeing area a . We will report the exponentiated coefficient as the relative risk estimate for unadjusted and adjusted models with their corresponding 95% confidence intervals.

We will examine non-linearity between age and the outcome by comparing the linear model with penalised smoothing splines³⁵ using a likelihood ratio test with the Wald method.³⁶ We will use the model with splines if it performs better than the linear model, using a p-value of 0.05 as the threshold for this decision.

We will examine potential effect modification by reporting stratified analyses by age, sex and educational level. If there are noticeable differences, we will test for multiplicative interactions between tobacco use and sex, age and educational level by including an interaction term in equation 1. We will introduce the interaction terms one by one for each of the examined interactions. We will use a likelihood ratio test to compare the model with and without the interaction. A p-value lower than 0.05 in the likelihood ratio test will be used as an indication of the presence of an interaction. If there is evidence of an statistically significant interaction, we will include the interaction term in the final model.

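### The plan's only model equation is introduced as estimating the risk of confirmed COVID-19, so as written no vaccination outcome has a specified model

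*Combined protocol and SAP*

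**What the plan says.** The aim, at the end of the introduction, is stated as "we will examine the association between tobacco use and COVID-19 vaccine uptake and between-dose spacing". The Outcomes section then says "Our primary outcome will be the vaccination uptake of at least two doses of a COVID-19 vaccine", followed by "We will examine four secondary outcomes": uptake of one or more doses, uptake of the full scheme including the booster, and two proportions with an interval above 7 months between successive doses. Infection is not on the list.

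Infection appears elsewhere, in a different role. Under the heading Potential mediators the plan says "We will obtain data on confirmed COVID-19 cases from the Finnish National Infectious Disease Register" and defines a confirmed case. The Confounding bias section adds "Having a COVID-19 infection, according to our DAG, would act as a mediator", and concludes that the main analyses should not adjust for it.

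The Statistical methods section opens with "We will use Poisson regression with robust standard errors to estimate the relative risk of confirmed COVID-19 cases" and gives Equation 1, a log-linear model, directly afterwards. The text below the equation explains the individual index, the intercept, the tobacco coefficient (it "is the coefficient of interest for exposure to tobacco"), the covariates and the area fixed effects. It does not say what the mean on the left-hand side is the mean of.

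**The concern.** The sentence that introduces Equation 1 is the only text that ties that equation to a response variable, and it names one that the plan does not list as an outcome. Followed literally, the main result would be a relative risk for tobacco use and infection. In the plan's own causal diagram that is the first arm of a mediated path, not the total effect of tobacco use on vaccination.

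The two quantities also read in opposite directions. A relative risk below 1 for infection would suggest fewer infections among tobacco users, whereas a relative risk below 1 for uptake would mean that tobacco users are less often vaccinated. A pre-specified plan should leave no doubt about which of these its primary model estimates.

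**Working it through.** No figure in the plan needs reproducing here, so the check is a comparison of the text.

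**1. Declared outcomes against the modelled outcome**

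| Section | Vaccination uptake or spacing | Confirmed infection |
|---|---|---|
| Study aim (end of introduction) | Subject of the study | Not mentioned |
| Outcomes | 1 primary + 4 secondary = 5 outcomes | Not listed |
| Potential mediators | – | Defined here |
| Confounding bias | End point of the causal diagram | Mediator; main analyses not adjusted for it |
| Statistical methods, sentence introducing Equation 1 | Not named | Named as the quantity estimated |

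**2. Does Equation 1 resolve it?** No. The terms on the right-hand side are explained, but the mean on the left is not.

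**3. Does later text resolve it?** Not explicitly. The spline comparison for age refers only to the outcome, without naming it. The interaction tests add terms to Equation 1 and so take over its response. The complete-case analysis and the analyses cut at 60% and 80% vaccination coverage repeat the main estimates without saying which response they have.

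**4. Is another model specified for uptake?** No. The Confounding bias section names marginal structural methods and the G-formula, but only for sensitivity analyses and without a model.

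**5. Count.** Written model equations: 1, of which 1 has infection as its stated response. Declared outcomes named as the response of a model in Statistical methods: 0 of 5.

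**6. Could the literal analysis be run?** Yes. Confirmed cases will be obtained from the infectious disease register, and the exposure and covariates come from the same linked surveys. Nothing would stop the model from fitting, and the output would be a tobacco relative risk with a 95% confidence interval in the format the plan asks for.

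**7. Are the two responses numerically alike?** No. The plan expects very few participants to be infected, while it reports 87.6% two-dose coverage in adults aged 18 and over. For illustration, suppose that uptake in the reference group equals that national figure. The relative risk for uptake could then not exceed 1 / 0.876 = 1.14. A relative risk for a rare infection has no such tight ceiling. One cannot stand in for the other.

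**The case against.** The strongest reply is that this is a slip in wording, and that the intended response is plain from everything around it. The aim concerns uptake. The causal diagram is titled for tobacco use and vaccination. The decision not to adjust the main analyses for infection makes sense only if infection is not the response. The Information bias section explains the occurrence of the outcome as vaccination. The sensitivity analyses are cut at levels of vaccination coverage. On this view the estimator is otherwise well described (Poisson regression, robust standard errors, covariates, area effects, survey weights, multiple imputation), only the label of the response is wrong, and no estimate would be biased because no analyst would follow the literal text.

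Most of this stands. Uptake was almost certainly intended, and the plan should not be read as a deliberate choice to model infection. It is also fair to say that the components of an estimator are present and that what is missing is their link to the declared outcomes.

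It does not dispose of the point. The evidence of intent confirms that the sentence is wrong, and the sentence is the operative rule for the primary analysis rather than background. Even on the charitable reading, nothing says that Equation 1 is fitted to each of the five outcomes, or who is in the denominator for the two spacing outcomes.

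**Conclusion.** The concern holds as stated and needs correcting before the analysis is run. As written, 1 of 1 specified models has a mediator as its response, and 0 of 5 declared outcomes is assigned a model. The contradiction lies within the current text, in a complete and legible sentence.

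The practical consequence depends on how the text is followed. If analysts follow the evident intent, the estimates are unaffected and the loss is in the clarity of the pre-specification. If they follow the sentence, the headline result does not answer the study question. The conclusion does not depend on the numerical illustration, which assumes that the reference group has the national two-dose coverage.

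**What to change.** In Statistical methods:

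- Reword the opening sentence so that the Poisson model with robust standard errors estimates the relative risk of each vaccination outcome, with receipt of two or more doses by the end of follow-up as the primary one.
- Define the mean in Equation 1 as the probability that the binary outcome equals 1 for individual i.
- State that Equation 1 is fitted separately to the primary and to each of the four secondary outcomes, and give the denominator for each. For the two spacing outcomes, say whether the denominator is all participants or only those who received both doses concerned. Carry over the exclusion of Janssen recipients from second-dose analyses that the Outcomes section already makes.
- State that confirmed infection enters only the sensitivity analyses named under Confounding bias.

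This costs a few lines of wording. It needs no new data, and it adds no analysis beyond those the Outcomes section already implies.

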FinSote surveys 2018 and 2020 are based on a stratified random sample design that represents the Finnish population. However, non-participation in the survey could potentially introduce nonresponse bias if participants are systematically different from non-participants. For this purpose, we will take into account the complex survey design in all analyses and use the inverse probability weights (IPW) created by the Finnish Institute for Health and Welfare using a model with register-based data for the whole sample on age, sex, marital status, educational level, mother tongue and place of residence. The IPW method allows correcting for survey non-participation and the weighting factor of each participant is a combination of the inverse of the participation probability and the sampling probability. Hence, the set of weighted coefficients represents the Finnish population.³⁴

Information bias

The risk of information bias from measurement error of the exposure and confounders is inherent to most population health surveys. However, our data is almost entirely collected before assessment of the outcome, reducing the possibility that the exposure is affected by the occurrence of the outcome (i.e. that COVID-19 vaccination affects tobacco use). COVID-19 vaccination in Finland started on December 27, 2020, with a focus on health and residential care workers. The number of doses available in the first months was limited, so it is unlikely that participants from FinSote 2020 received the vaccination before the data collection. As sensitivity analyses, we will carry out the same analyses but excluding participants who have received a vaccination dose prior to February 8, 2021, when the data collection of FinSote 2020 ended. In addition, smoking status was collected relatively close to the COVID-19 vaccination, reducing (although not excluding it completely) the risk of exposure misclassification.

The COVID-19 vaccination has been implemented nationally by public providers, meaning that all COVID-19 vaccines provided have been registered in the Finnish National Vaccination Register. We estimate the risk of loss to follow-up and information bias of the outcome to be close to zero.

Study size

The sample size was determined by the available data from FinSote surveys 2018 and 2020. We consider it not necessary to provide a sample size calculation.

Quantitative variables

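### Age stays linear unless an under-specified p<0.05 test selects splines; entering a spline in every adjusted model costs nothing and removes the choice

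*Combined protocol and SAP*

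**What the plan says.** Under Quantitative variables the plan states "We will model age as a continuous variable" and compares a linear form with penalised smoothing splines by a likelihood ratio test. Under Statistical methods, directly after equation (1), it repeats the comparison but describes the test as "using a likelihood ratio test with the Wald method". The decision rule follows: "We will use the model with splines if it performs better than the linear model, using a p-value of 0.05 as the threshold".

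Three other statements bear on the test:
- The model is described as "We will use Poisson regression with robust standard errors".
- Under Selection bias the plan says "we will take into account the complex survey design in all analyses", including the non-response weights.
- Under Statistical methods: "We will examine potential effect modification by reporting stratified analyses by age, sex and educational level".

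The plan does not give the degrees of freedom of the spline or the variance used in the test. It does not say whether the test is repeated by outcome, exposure or stratum, or how it is carried out with multiply imputed data.

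**The concern.** Age is a confounder in every adjusted model. The rule treats a non-significant test as evidence that a line is adequate. That is only reasonable if the test has good power, and the power depends on which statistic is computed.

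The gate also buys nothing. A penalised spline already shrinks towards a line when a line fits, and its few degrees of freedom are negligible among thousands of records.

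If the test has little power and is run separately in each model, some strata could be adjusted with a spline and others with a line. Stratum-specific tobacco RRs, which the plan inspects before deciding whether to test interactions, would then carry unequal residual confounding by age.

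**Working it through.** The plan states no power or error rate for this test, so there is no figure of its own to reproduce.

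**Inputs from the documents**
- Analytical samples of 14,736 (FinSote 2018) and 28,199 (FinSote 2020): 14,736 + 28,199 = 42,935.
- Two-dose coverage of 87.6% in adults (background section).
- Test threshold of 0.05.

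**Assumptions**
- Equation (1) applies to the vaccination outcomes, although the sentence introducing it names confirmed infections.
- Sex strata hold about 42,935/2 ≈ 21,468 people and education tertiles about 42,935/3 ≈ 14,312.
- The design effect is 1.0 or 1.5.
- All uptake-by-age and tobacco-by-age curves are assumed.

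**Step 1: scale of an ordinary Poisson likelihood ratio.** A binary outcome with mean p has variance p(1 − p), but the Poisson likelihood assumes variance p. The statistic is therefore about (1 − p) times a correctly scaled one:
- 1 − 0.876 = 0.124, so it is about 1/0.124 ≈ 8 times too small.
- The nominal 1-df critical value of 3.84 corresponds to 3.84/0.124 ≈ 31.0 on the proper scale. The actual size is then P(χ²₁ > 31.0) ≈ 3 × 10⁻⁸ instead of 0.05.
- Curvature must be about √8.06 ≈ 2.8 times larger to give the same expected statistic.

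Robust standard errors on the tobacco coefficient do not repair this, because an ordinary likelihood ratio does not use them.

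**Step 2: how often splines are selected.** Poisson models were simulated for two-dose uptake, with linear age against a fixed-df natural cubic spline (4 or 8 df) standing in for the penalised spline. Overall uptake was about 0.88 to 0.90, the true smoking RR was 0.97, and there were 80 to 150 runs per setting. Entries are the proportion of runs selecting splines.

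| n | Assumed curvature | Ordinary Poisson LR | Robust Wald | Robust Wald, design effect 1.5 |
|---|---|---|---|---|
| 14,312 | mild | 0.00 | 0.38–0.81 | 0.10–0.56 |
| 14,312 | moderate | 0.00–0.01 | 1.00 | 0.97–1.00 |
| 14,312 | strong | 0.05–0.87 | 1.00 | 1.00 |
| 21,468 | mild | 0.00 | 0.75–0.93 | 0.31–0.81 |
| 21,468 | moderate | 0.00–0.14 | 1.00 | 1.00 |
| 21,468 | strong | 0.55–1.00 | 1.00 | 1.00 |
| 42,935 | mild | 0.00 | 0.96–1.00 | 0.71–1.00 |
| 42,935 | moderate | 0.04–0.99 | 1.00 | 1.00 |
| 42,935 | strong | 1.00 | 1.00 | 1.00 |

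As a check on step 1, the ratio of mean likelihood ratio to mean robust Wald statistic at 42,935 (4 df) was 2.4/24.8 = 0.10 under mild curvature, 8.8/103.9 = 0.08 under moderate and 26.5/263.8 = 0.10 under strong. That is the same order as 0.12.

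A second simulation used other assumed curves, a true RR of 0.93 and 30% aged 75 or over. The ordinary likelihood ratio selected splines in 0–27% of tertile-size runs for three curves and 62% for a fourth. In sex strata it did so in 40–81%, and 97% for the fourth. It always did so at 42,935. A robust Wald test selected splines in every run of the three curves tried. For booster uptake splines were always selected.

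**Step 3: what keeping the line does to the smoking RR**
- First simulation, where the likelihood ratio mostly kept the line in strata: a shift of 0.001–0.003 towards 1, about 0.1–0.35 SE. The SE is about 0.008 in a sex stratum and 0.010 in a tertile.
- Second simulation: about 0.003–0.006 towards 1, or 0.26–0.51 SE at tertile size.
- A third set of assumed curves gave about 0.001–0.004, roughly 0.1–0.4 SE in the strata.
- A snus-like exposure at ages 20–74: at most about 0.001, against an SE of 0.018–0.023.

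**Step 4: effect on coverage.** With a bias of b standard errors, a nominal 95% interval covers with probability Φ(1.96 − b) − Φ(−1.96 − b). For b = 0.25 this is 0.943, for b = 0.35 it is 0.936, and for b = 0.51 it is 0.920. Simulated coverage ranged from 0.90 to 0.97 both after the pre-test and with splines always used. Too few runs were made to separate differences of this size.

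**The case against.** The strongest reply is that the unfavourable result depends on one reading of the test. The plan names a Wald method, uses robust standard errors and applies the survey design throughout. An unweighted, model-based Poisson likelihood ratio is the reading that fits this text least well. With a robust Wald test, moderate or strong curvature is detected in 97–100% of all-age strata, and what is missed is mild curvature that leaves little bias. The test is described once, straight after equation (1), and nothing says it is repeated by stratum. If the form is chosen once, strata cannot differ in it. Formal effect modification rests on an interaction term, not on a comparison of stratum RRs. Finally, the plan does anticipate non-linearity and specifies in advance a method and a threshold.

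Most of this stands. A reader might infer that the planned test often keeps the line in the strata and leaves material confounding. The documents do not support that, because it needs both the ordinary likelihood ratio and testing within strata, and the text settles neither. A reader might also infer that the pooled primary RR is safe whatever test is used. That is too firm: with the ordinary likelihood ratio at 42,935, splines were selected in none of the mild-curvature runs and in 4–99% of the moderate ones.

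What survives is the ambiguity. The two descriptions of the test can lead to opposite decisions on the same data, and the default gives way only if the test rejects.

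**Conclusion.** The rule makes a straight line the default for age, and the test that can overturn it is not defined well enough to know its power. On the ordinary likelihood ratio reading the line can often be kept under mild or moderate curvature. On the robust, design-based Wald reading splines would usually be chosen unless curvature is mild.

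The size is small either way: about 0.001–0.004 on the smoking RR, 0.006 at the most, and no more than about half a standard error. Coverage would fall from 95% to roughly 92% in the worst of these cases. The direction towards 1 holds for smoking under the curves tried; a steeper age pattern could enlarge the shift.

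These figures rest on assumed age curves, stratum sizes and design effects. The simulations did not include the actual weights, penalty, other covariates or imputation. This is a free improvement in specification, not a defect that puts the main conclusions in doubt.

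**What to change.** - Enter age as a spline in every adjusted pooled, sex-stratified, education-stratified and sensitivity model. Use either the penalised spline already named or a natural cubic spline with knots fixed in advance.
- In the age-stratified models, keep age as a continuous term within the stratum, with a spline only where the stratum is wide.
- Delete the linearity test and its 0.05 threshold as a decision rule. If it is reported at all, report it descriptively with a robust, design-based variance.
- Use the same wording under Quantitative variables and Statistical methods.

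If the test is kept as a gate, the least that is needed is to name a robust, design-based statistic and say at what level it is applied.

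The cost is a change of wording. It removes one analysis step, needs no new data and uses a few degrees of freedom among thousands of records.
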